9.5. Pharmacokinetics

9.5.1. Blood Sampling and Processing

For all patients, serial blood samples will be collected on Day 1 and Day 28 of Treatment Period 1 for the determination of plasma concentrations of GLWL-01. Sample collection time points are specified in the Schedule of Activities ([Section 2](#)). Times of sampling are intended as a guide and may be modified to accommodate clinical procedures. The actual date and time (24-hour clock time) of each sample collection will be recorded. The date and time of dosing on the days of PK sample collection will also be recorded. Instructions for the collection and handling of blood samples will be provided by the sponsor in a separate document.

A maximum of 2 samples may be collected at additional time points during the study if warranted and agreed upon between both the investigator and sponsor. For patients who discontinue early, a PK sample should be taken at the early termination visit.

Drug concentration information that may unblind the study will not be reported to investigative sites or blinded personnel until the study has been unblinded. Placebo samples are not planned to be assayed.

9.5.2. *Bioanalytical Method*

Plasma sample bioassays of GLWL-01 will be performed using validated procedures and methods at a laboratory approved by the sponsor. Placebo samples will be shipped to the laboratory in order to maintain the blind, and are not planned to be assayed.

Bioanalytical samples collected to measure study drug concentration will be retained for a maximum of 1 year following last patient visit for the study.

9.6. Pharmacodynamics

9.6.1. *Acylated-Ghrelin and Unacylated-Ghrelin*

A separate PD sampling manual will detail the appropriate collection and processing procedures to be followed for this study. For all patients, blood samples for the determination of PD assessments (AG and UAG) will be collected at scheduled time points as provided in Schedule of Activities (Section 2). The blood samples should be collected in a fasted state.

9.7. Biomarkers

Not applicable.

9.8. Health Economics

Not applicable.

10. Statistical Considerations

10.1. Sample Size Determination

Approximately 34 patients will be randomized to 1 of 2 treatment sequences (GLWL-01/placebo or placebo/GLWL-01) in a 1:1 ratio. Thirty-four patients will provide approximately 80% power to detect an effect size of 0.75 for the HQ-CT total score using a 2-sided exact paired t-test with an $\alpha=0.05$, assuming 10% drop out.

10.2. Populations for Analyses

For purposes of analysis, the following populations are defined:

Analysis Set	Description
Entered	All patients who sign informed consent
Randomized	All randomized patients who take at least 1 dose of double-blind study drug. Patients will be analyzed according to the treatment they actually received.

10.3. Statistical Analyses

10.3.1. General Statistical Considerations

Statistical analysis of this study will be the responsibility of GLWL Research Inc. or its designee.

Efficacy analyses will be conducted on the randomized analysis set. This set includes all data from all randomized patients receiving at least 1 dose of double-blind study drug. Patients will be included in the analysis if they have a postbaseline measurement for the parameter being analyzed. Safety analyses will be conducted on the randomized analysis set. Patients will be analyzed according to the study drug they actually received.

Data will be presented using summary tables by treatment, unless otherwise specified.

Continuous data will be summarized using the mean, standard deviation, median (for selected variables), minimum, and maximum. Categorical data will be summarized as frequency counts and percentages. Figures may be used to support the presentation of selected data.

All tests of treatment effects will be conducted at a 2-sided alpha level of 0.05, unless otherwise stated.

Baseline values will be defined as the last available value prior to receiving double-blind study drug for each double-blind treatment phase.

For the purposes of follow-up analyses, the first 2 weeks of the washout period will be the follow-up for the Treatment Period 1 double-blind treatment phase and the Follow-up Period will be the follow-up for the Treatment Period 2 double-blind treatment phase.

Details related to handling of missing data will be described in the statistical analysis plan (SAP).

Any change to the data analysis methods described in the protocol will require an amendment only if it changes a principal feature of the protocol. Any other change to the data analysis

methods described in the protocol, and the justification for making the change, will be described in the SAP and/or in the clinical study report (CSR).

Additional exploratory analyses of the data will be conducted as deemed appropriate.

10.3.2. Treatment Group Comparability

10.3.2.1. Patient Disposition

All patients who discontinue from the study will be identified, and the extent of their participation in the study will be summarized by treatment sequence. If known, a reason for their discontinuation will be given.

10.3.2.2. Patient Characteristics

Patient demographics (age, gender, race, ethnicity, height, weight, and BMI) will be summarized by treatment sequence for the safety analysis set.

10.3.2.3. Concomitant Therapy

Concomitant therapy will be listed.

10.3.2.4. Treatment Compliance

Treatment compliance will be calculated for each double-blind treatment phase as

$$\text{Treatment Compliance} = \frac{\text{number of capsules received}}{\text{number of intended capsules}} * 100$$

10.3.3. Efficacy Analyses

10.3.3.1. Primary Analyses

The primary analysis will be conducted using a restricted maximum likelihood-based, mixed-effect model repeated measures analysis. The analysis of the primary endpoint will be the contrast between GLWL-01 and placebo at the end of the double-blind treatment phase on the posttreatment HQ-CT score.

The model for the primary analysis will include the fixed, categorical effects of sequence, period, and treatment, as well as the continuous, fixed covariate of the baseline double-blind Treatment Period 1 phase HQ-CT score minus the baseline double-blind Treatment Period 2 phase HQ-CT score (diff) and the interaction of period*diff (Mehrotra 2014).

An unstructured covariance structure will be used to model the within-patient errors.

Sensitivity analyses will be outlined in the SAP.

10.3.3.2. Secondary Analyses

The secondary analysis will be conducted similarly to the primary analysis, but the model will not include the baseline covariate or interaction. The secondary efficacy endpoint is the CGIC.

10.3.3.3. Exploratory Analyses

The following exploratory endpoints will be analyzed using the same methodology as for the primary efficacy analysis:

- AG
- UAG
- AG/UAG ratio
- Body weight
- Percentage fat mass
- BMI
- Waist circumference
- low-density lipoprotein
- Total cholesterol

10.3.4. Safety Analyses

The safety analyses will be conducted for the double-blind treatment phase and follow-up combined. Data will be summarized by treatment group unless otherwise noted.

The safety and tolerability of treatment will be assessed by evaluating the following:

- Treatment-emergent adverse events by Preferred Term and maximum severity
- SAEs
- AE leading to discontinuation
- Suicidal ideation and behaviours assessed by solicited questioning using the C-SSRS
- Vital signs and weight
- ECGs
- Laboratory measurements

Treatment-emergent adverse events are defined as the reported AEs that first occurred or worsened during the double-blind treatment phase and follow-up compared with baseline. The most recent version of Medical Dictionary for Regulatory Activities Lowest Level Term (LLT) will be used in the treatment-emergent computation. For each LLT, the maximum severity at baseline will be used as the baseline severity. If the maximum severity during postbaseline is greater than the maximum baseline severity, the event is considered to be treatment emergent for the specific postbaseline period. Treatment-emergent adverse events will be summarized by the number and percentage of patients with the event.

For events that are gender-specific, the denominator and computation of the percentage will include only patients from the given gender.

Suicidal ideation, suicidal behavior, and nonsuicidal self-injurious behavior based on the C-SSRS will be listed.

Vital signs collected during the study include systolic and diastolic BP, pulse, and temperature. Blood pressure and pulse measurements will be taken when the patient is in a sitting position. Three measurements of sitting BP will be collected at approximately 30- to 60-sec intervals and those 3 sitting BP will be averaged and used as the value for that visit for analysis.

The incidence rates of patients with clinically significant vital sign and weight changes at any time postbaseline will be assessed using Fisher's exact test. The clinically significant criteria will be documented in the SAP.

The QT and QTcF interval will be summarized with the number and percentage of patients with values >450 msec, >480 msec, and >500 msec at any time postbaseline.

The incidence rates of patients with treatment-emergent abnormal, high, or low laboratory values at any time postbaseline will be assessed using Fisher's exact test for each laboratory test.

Patients will be defined as having a treatment-emergent low value if they have all normal or high values at baseline, followed by a value below the lower reference limit at any postbaseline visit. Patients with all normal or high values at baseline (no low values) will be included in the analysis of treatment-emergent low laboratory values. Patients will be defined as having a treatment-emergent high value if they have all normal or low values at baseline, followed by a value above the upper reference limit at any postbaseline visit. Patients with all normal or low values at baseline (no high values) will be included in the analysis of treatment-emergent high laboratory values.

For analytes simply classified as normal or abnormal, patients will be defined as having a treatment-emergent abnormal value if they have all normal values at baseline, followed by an abnormal value at any postbaseline visit. Patients with all normal values at baseline will be included in the analysis of treatment-emergent abnormal laboratory values.

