- b. Have evidence of other chronic liver disease, including but not limited to chronic alcoholic disease, cirrhosis of any cause, recent history (within 3 months of screening) of acute viral hepatitis or chronic autoimmune hepatitis. Patients with a history of biliary disease, including primary sclerosing cholangitis, must be excluded. Patients with a history of cholecystectomy longer than 6 months prior to screening could be enrolled.
- c. Have evidence of significant active or unstable/uncontrolled psychiatric disease by medical history, such as bipolar disorder, schizophrenia, personality disorders, or other serious mood or anxiety disorders. Note: Patients whose disease state is considered stable and expected to remain stable throughout the course of the study, in the opinion of the investigator, may be considered for inclusion if they are not on excluded medications.

18. Have an abnormality in the 12-lead electrocardiogram (ECG), including corrected QT interval with Frederica's correction ($QTcF$) >450 msec for men and >470 msec for women or an abnormality that, in the opinion of the investigator, increases the risks associated with participating in the study. If $QTcF$ does not meet criteria, ECGs may be repeated once after 5 minutes of rest.

19. Have a family history of Long QT Syndrome.

20. Have evidence of human immunodeficiency virus (HIV) infection, hepatitis B, hepatitis C and/or positive results at screening for the respective antibodies for HIV, hepatitis B surface antigen, or hepatitis C antibodies.

21. Patients who, in the clinician's judgment, are actively suicidal and therefore deemed to be at significant risk for suicide, or those who have answered "yes" to either Question 4 (Active Suicidal Ideation with Some Intent to Act, Without Specific Plan) or Question 5 (Active Suicidal Ideation with Specific Plan and Intent) on the "Suicidal Ideation" portion of the Columbia–Suicide Severity Rating Scale (C–SSRS), or answer "yes" to any of the suicide-related behaviors (actual attempt, interrupted attempt, aborted attempt, preparatory act or behavior) on the "Suicidal Behavior" portion of the C–SSRS; and the ideation or behavior occurred within a month of Visit 1.

22. Patients on weight loss medications within 30 days of dosing. Patients with a history of bariatric surgery should also be excluded.

23. Unable to refrain from or anticipates the use of

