7.7. Concomitant Therapy

Patients may not take any medication (including over-the-counter products), herbal products, or vitamin supplements, which are CYP3A and/or P-gp inhibitors for 14 days prior to dosing and throughout the study. In cases that require the use of such medication for the treatment of an AE or comorbidity, GLWL-01 dosing must be terminated before the CYP3A inhibitor can be started.

Medications that prolong the QT/QTc interval are allowed provided the patient has been on a stable dose of said medication for at least 3 months and has a QTc < 450 msec at Visit 1 and Visit 3. A list of medications with a potential for QTc prolongation will be provided separately to the investigators.

If the need for the initiation of other medication arises during the study, the investigator must consult with sponsor medical representative and such medication change must be reported in the EDC.

All medications taken by patients during the course of the study will be recorded. Concomitant medications will be listed by treatment and coded using the most current World Health Organization drug dictionary.

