### **7.5. Electrocardiogram Summaries**

Single 12-lead electrocardiograms (ECGs) will be assessed during screening; on Treatment Phase Day 0 (i.e. Baseline), Treatment Phase Day 7, and Treatment Phase Day 28 of each treatment phase; and at a patient's early termination visit, if applicable. Two-hour post-dose ECG assessments will also be made at Baseline of each treatment phase.

The number and percent of patients with any post-baseline Fridericia-corrected QT values of potential clinical interest (including unscheduled and early termination assessments) will be summarized. QTcF values of potential clinical interest will be determined using the following criteria:

- QTcF  $\geq$  480 msec, or  $\geq$  500 msec, or  $\geq$  550 msec
- Change from baseline in QTcF  $\geq$  30 msec, or  $\geq$  60 msec.

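### SAP 7.5 drops the protocol's >450 msec QTcF count and the uncorrected QT summary without listing the change, leaving a partial gap in the 451–479 msec range

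*Protocol*

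**What the plan says.** Protocol 10.3.4 fixes the ECG outlier summary. For both QT and QTcF it calls for the "number and percentage of patients with values >450 msec, >480 msec, and >500 msec at any time postbaseline". In the same section the cut-offs for vital signs and weight are left to the SAP. The QT cut-offs are not.

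SAP 7.5 covers "The number and percent of patients with any post-baseline Fridericia-corrected QT values of potential clinical interest", including unscheduled and early-termination readings. Its absolute criteria are "QTcF $\geq$ 480 msec, or $\geq$ 500 msec, or $\geq$ 550 msec" and its relative criteria are "Change from baseline in QTcF $\geq$ 30 msec, or $\geq$ 60 msec". It has no 450 msec category and no summary of uncorrected QT.

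SAP 2.9 records four departures from the protocol: the renamed analysis population, the addition of blood glucose, the new way of determining treatment-emergent adverse events, and the move to 1-sided tests. It does not mention QT or QTcF.

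The 450 msec figure appears elsewhere in the protocol as an entry limit. Exclusion 18 in section 6.2 uses QTcF ">450 msec for men and >470 msec for women or an abnormality" of other kinds. A patient on a QT-prolonging drug may take part only on a stable dose and if he or she "has a QTc < 450 msec at Visit 1 and Visit 3" (section 7.7, and likewise exclusion 23c).

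**The concern.** A safety count that the protocol specified in advance will not be produced under the SAP as written, and a reader of the SAP cannot tell whether that was a decision or an oversight. SAP 2.9 is detailed enough to record a change of population name, so silence on a dropped safety category is easily read as no change.

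The dropped category is the lowest absolute one. It is also the level that men, and patients of either sex on QT-prolonging drugs, had to satisfy at entry. The SAP is written for protocol version (d), which admits patients on stable QT-prolonging drugs. At stake is whether a modest rise past the entry level appears in the tables by treatment or only in individual data.

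**Working it through.** There is no stated figure to reproduce. The check sets the two rules side by side and then finds which changes in QTcF fall between them.

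**Rules compared**

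| | Protocol 10.3.4 | SAP 7.5 |
|---|---|---|
| Interval | QT and QTcF | QTcF only |
| Absolute categories (msec) | >450, >480, >500 | ≥480, ≥500, ≥550 |
| Change from baseline (msec) | none | ≥30, ≥60 |
| Window | any post-baseline value | any post-baseline value |

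**Condition for a missed crossing of 450.** Let b be the baseline for the treatment phase and p a post-baseline value, in whole msec. The patient has b ≤ 450 and p > 450, and meets no SAP criterion when p < 480 and p − b < 30. So p lies between 451 and the smaller of 479 and b + 29. The range is non-empty only if b + 29 ≥ 451, that is b ≥ 422. Missed crossings are therefore possible from baselines of 422–450.

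| Baseline | Values above 450 in no SAP category |
|---|---|
| 421 or lower | none (451 − 421 = 30, so the change criterion applies) |
| 430 | 451–459 |
| 440 | 451–469 |
| 445 | 451–474 |
| 449 | 451–478 |
| 450 | 451–479 |

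**Examples**
- 440 to 465: change 25. Counted by the protocol (>450), in no SAP category.
- 449 to 477: change 28. Same result.
- 420 to 452: change 32. Counted by the SAP through the ≥30 criterion.
- 400 to 440: change 40. Counted by the SAP, not by the protocol.

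**The 470 limit for other women.** The same argument with p > 470 gives missed values of 471–479 when the rise is under 30, possible from a baseline of 442 (471 − 29) upwards.

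**Discontinuation values.** Protocol section 8 names >500 msec, or >60 msec over baseline. The SAP's ≥500 and ≥60 categories contain both.

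**Inequality sign.** Replacing > with ≥ matters only for a reading of exactly 480 or 500 msec, and there the SAP counts slightly more.

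**Effect of adding QTcF >450 to the SAP.** Every post-baseline value above 450 is then counted. The uncounted region is empty for the 450 level, and so for the 470 level as well.

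**The case against.** The strongest case for the SAP is that its criteria are in one respect better. Change-from-baseline categories pick up rises that stay wholly below 450 msec, which the protocol's categories cannot do. This stands, and it is why the change criteria should be kept. It also rules out the inference that an early signal could only appear between 450 and 480 msec.

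A reader might infer that 450 msec is the trial's limit for patients on treatment. The documents do not support that. It is an eligibility value, and not for everyone: women not on QT-prolonging drugs may enter at up to 470. The on-study values are those in protocol section 8, which the SAP still tabulates.

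A reader might also infer that every patient with a maximum of 451–479 msec and a rise under 30 is a missed prolongation. That is too wide. A woman who enters at 460 and stays there has crossed nothing, yet the protocol's >450 category, which has no baseline condition, would count her under both treatments. The category alone mixes entry values with new crossings.

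Nor is the information lost. SAP section 2 puts all eCRF data into the datasets, and the protocol synopsis promises listings and descriptive statistics for ECG parameters. SAP section 9 plots QTcF change against concentration. That plot is only partial cover, because scheduled PK sampling is confined to Treatment Period 1 and early termination. None of these is a count by treatment.

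Finally, protocol 10.3.1 allows a change that does not alter a principal feature to be described in the SAP and/or the clinical study report. The omission from SAP 2.9 is therefore not yet a breach. It remains an unexplained difference at the point where a reader would look for it.

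**Conclusion.** The mismatch is real and unlisted. It removes one QTcF category and the whole uncorrected QT summary. For QTcF the consequence is limited to crossings of 450 msec that end at 451–479 with a rise under 30, from whole-msec baselines of 422–450. With the 19 patients anticipated in SAP 2.9, one such patient would be 1/19, or about 5%.

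How many patients will fall in this region cannot be stated, because neither document gives a QTcF distribution. For the same reason it would be wrong to predict that the 480, 500 and 550 categories will be empty, or that a 450 category will be informative. The summary of amendment (c) reports no QT/QTc prolongation to that date, which settles neither question.

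The result assumes whole-msec readings and a baseline taken separately for each treatment phase, as SAP 2.3 defines it. The primary efficacy analysis is unaffected. This is a consistency repair to a descriptive safety table, and worth making because it is cheap and restores what was specified in advance.

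**What to change.** In SAP 7.5:

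- Add a row for QTcF >450 msec by treatment. Keep the existing absolute categories and the change criteria.
- Preferably add a second row for new crossings: baseline at or below 450 and a post-baseline value above 450 in the same treatment phase, among patients whose baseline is at or below 450. This separates new crossings from women who entered at 451–470. Protocol 10.3.4 already uses the same construction for treatment-emergent high laboratory values.
- Either restore the three uncorrected QT rows (>450, >480, >500 msec) or state and justify their removal in SAP 2.9.

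In SAP 2.9, list whatever differences remain, including the added 550 msec level, the change criteria and the use of ≥ in place of >.

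The cost is at most 1 + 1 + 3 = 5 extra rows in an existing descriptive table, plus a short entry in 2.9. The ECGs are already scheduled, so no new data are needed.

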10.3.5. Pharmacokinetic/Pharmacodynamic Analyses

Plasma GLWL-01 PK parameters will be calculated using noncompartmental methods after single and multiple dose administration (on Day 1 and Day 28 of Treatment Period 1, respectively). Additional PK parameters may be calculated if deemed appropriate.

Pharmacokinetic parameters will be summarized by dose level using descriptive statistics. Mean and individual GLWL-01 plasma concentration-time curves will be represented graphically.

Accumulation will be estimated. Additional analyses will be performed as deemed necessary upon review of the data.

Pharmacokinetic data may be fit with a population PK model; and may be pooled with data from previous studies.

Pharmacodynamics of GLWL-01 will be based on plasma AG and potentially UAG measures. Raw and change from baseline values will be reported and summarized for AG and potentially UAG.

The PK/PD relationship of GLWL-01 with PD, efficacy, and/or safety measures may be explored.

10.3.6. Evaluation of Immunogenicity

Not applicable.

Appendix 1. Abbreviations and Definitions

Term	Definition
AE	adverse event: Any untoward medical occurrence in a patient or clinical investigation patient administered a pharmaceutical product that does not necessarily have a causal relationship with this treatment. An adverse event can therefore be any unfavorable and unintended sign (including an abnormal laboratory finding), symptom, or disease temporally associated with the use of a medicinal (investigational) product, whether or not related to the medicinal (investigational) product.
AG	acylated-ghrelin
ALP	alkaline phosphatase
ALT	alanine aminotransferase
AST	aspartate aminotransferase
BID	twice a day
blinding	A double-blind study is one in which neither the patient/caregiver nor any of the investigator or sponsor staff who are involved in the treatment or clinical evaluation of the patients are aware of the treatment received.
BMI	body mass index
BP	blood pressure
CGIC	Caregiver Global Impression of Change
complaint	A complaint is any written, electronic, or oral communication that alleges deficiencies related to the identity, quality, purity, durability, reliability, safety or effectiveness, or performance of a drug or drug delivery system.
compliance	Adherence to all study-related, good clinical practice (GCP), and applicable regulatory requirements.
CSR	clinical study report
C-SSRS	Columbia–Suicide Severity Rating Scale
CYP	cytochrome P450
ECG	Electrocardiogram
EDC	electronic data capture
enroll	The act of assigning a patient to a treatment. Patients who are enrolled in the study are those who have been assigned to a treatment.

enter	Patients entered into a study are those who sign the informed consent form directly or through their legally acceptable representatives.
ERB	ethical review board
FSH	follicle-stimulating hormone
GCP	good clinical practice
GGT	gamma-glutamyl transferase
GHSR-1a	growth hormone secretagogue receptor
GOAT	ghrelin-O-acyltransferase
HIV	human immunodeficiency virus
HQ-CT	Hyperphagia Questionnaire for Clinical Trials
IB	Investigator's Brochure
ICF	informed consent form
ICH	International Council for Harmonisation
informed consent	A process by which a patient voluntarily confirms his or her willingness to participate in a particular study, after having been informed of all aspects of the study that are relevant to the patient's decision to participate. Informed consent is documented by means of a written, signed, and dated informed consent form.
IWRS	interactive web-response system
LLT	Lowest Level Term
P-gp	P-glycoprotein
PI	principal investigator
PK/PD	pharmacokinetic(s)/pharmacodynamics
PWS	Prader-Willi syndrome
QD	once daily
QTcF	corrected QT interval with Frederica's correction
SAE	serious adverse event
SAP	statistical analysis plan
screen	The act of determining if an individual meets minimum requirements to become part of a pool of potential candidates for participation in a clinical study.

study drug	A pharmaceutical form of an active ingredient or placebo being tested or used as a reference in a clinical trial, including products already on the market when used or assembled (formulated or packaged) in a way different from the authorized form, or marketed products used for an unauthorized indication, or marketed products used to gain further information about the authorized form.
SUSAR	suspected unexpected serious adverse reaction
TBL	total bilirubin level
TEAE	treatment-emergent adverse event: An untoward medical occurrence that emerges during a defined treatment period, having been absent pretreatment, or worsens relative to the pretreatment state, and does not necessarily have to have a causal relationship with this treatment.
UAG	unacylated-ghrelin
ULN	upper limit of normal

